3.14.1 Subgroup Analyses

For the primary efficacy endpoint (change from baseline in FEV₁ percent predicted from baseline to week 24, for the overall cohort), descriptive subgroup analyses will be performed for the stratification category(ies) included in the repeated measures analysis, the baseline use of Trikafta (yes versus no) and the effect of the pandemic confinement (pre versus post pandemic onset), described above in [Section 3.14](#).

The effect of the pandemic confinement will be assessed with a dichotomous variable defined as pre versus post pandemic onset. More specifically, the pre-pandemic group will include all patients who completed their Day 161 visit or discontinued from the study before in-person visits were jeopardized and confinement was initiated at the end of March 2020, while all other patients will be included in the post-pandemic onset group.

For the purposes of the analyses, the cut-off date will be set to March 31st, 2020. Patients completing their Day 161 visit or discontinuing from the study after March 31st, 2020 will be considered as having been affected by the pandemic confinement.

Additional post-hoc analyses may be performed in an exploratory manner depending on the frequency of other phenotypes or concomitant health conditions/drugs.

3.14.2 Sensitivity Analyses- Primary Efficacy Endpoint

In the analysis of the primary efficacy endpoint, the absolute change from Baseline in FEV₁ percent predicted will be repeated to include all measurements up to Week 24 and will be performed according to the specifications described in [Section 3.14](#) above.

In addition, though no imputations will be used in the primary analysis, a sensitivity analysis will be conducted for the analysis of the primary endpoint (change from baseline in FEV₁ percent predicted from baseline to week 24, for the ITT cohort), when > 5% of data points in each group have missing information for the change in FEV₁ predicted from baseline to week 24 (<57 patients per group have information). Missing data points will be imputed using a multiple imputation method. This method will generate m completed data sets ($m=5-20$), each with the observed values and different plausible values imputed for the missing observations. Each data set is analyzed using usual methods and the results are then combined across the analyses.

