12.4 Efficacy Analysis

12.4.1 Analysis of Primary Endpoint

The study will be considered successful if a statistically significant advantage for fenretinide over placebo is obtained for the absolute change in FEV₁ percent predicted from baseline to Week 24.

Values for percent predicted FEV₁ as well as their change relative to baseline will be tabulated by time point and descriptive statistics will be used. In the analysis for the primary efficacy endpoint, change from baseline in FEV₁ % predicted (absolute change), including all measurements up to Week 28 (both during and after treatment measurements, including after treatment discontinuation) will be analyzed based on a mixed-effect repeated-measure model. Even though no imputations will be used in the primary analysis, a sensitivity analysis will be conducted where missing data points will be imputed using appropriate interpolation methods; extrapolation methods will be used for truncated FEV₁ % predicted values.

The planned model will include the absolute change from baseline in FEV₁ % predicted as the dependent variable; treatment, visit, and treatment-by-visit interaction as fixed effects; and patient as a random effect with adjustments for a) FEV₁ % predicted determined at the Screening/Baseline Visits (average where possible), b) PEx frequency in the prior year, and c) Co-administration or not of Kalydeco® (ivacaftor), Orkambi® (ivacaftor/lumacaftor), Symdeko® (ivacaftor/tezacaftor) or another commercially available CFTR modulator product. Additional post-hoc analyses may be performed in an exploratory manner depending on the frequency of other phenotypes or concomitant drugs. The primary result obtained from the model will be the treatment effect at Week 24. The estimated mean treatment effect, a 95% confidence interval, and a 2-sided P value will be generated. Alternative methods will be used if necessary due to data not meeting the standard requirements for the proposed analysis.

Full details will be specified in the SAP.

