3 STATISTICAL METHODS

3.1 Statistical Handling Policy

3.1.1 Analysis Conventions

This section details general guidelines to be used for the statistical analyses. Deviations from these general policies may be given in the specific detailed sections of this statistical analysis plan. When this situation occurs, the rules set forth in the specific section take precedence over the general conventions. The following policies will be applied to all data presentations and analyses:

- Two-tailed tests will be performed for all analyses that use statistical testing with a significance level of $\alpha = 0.05$
- All p-values will be rounded to 4 decimal places (SAS format p-value). All p-values that round to 0.000 will be presented as '<0.001' and p-values that round to 1.000 will be presented as '>0.999'.
- Summary descriptive statistics will consist of the number and percentage of responses in each category for discrete variables, and the mean, median, standard deviation (SD), minimum, maximum, and 95% confidence interval for continuous variables.
- All mean and median values will be formatted to one decimal place. Standard deviation values will be formatted to two decimal places.
- All percentages will be rounded to one decimal place. Where appropriate, the number and percentage of responses will be presented in the form XX (XX.X %), where the percentage is in the parentheses.
- All listings will be sorted for presentation in order of treatment group, site number, subject number, and date of procedure or event.
- When necessary for analysis purposes, partial dates will be completed (i.e., turned into complete dates) using the most conservative approach. Where appropriate, all analyses and summary tables will have the population sample size for each treatment group in the column heading.

- Tables will include titles with the corresponding analysis population and footnotes describing the analyses involved, and listings of covariates included in the analyses, where relevant.
- In order to maintain vertical alignment, all tables and listings will be incorporated into MS Word and an 8-point Courier New font will be used.
- Version 9.4 (or later) of SAS® will be the statistical software package used to produce all summaries, listings, statistical analyses, and graphs.
- Version 20.0 (or higher) of MedDRA will be used for adverse event and pre-treatment conditions coding.

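### The imputation-based sensitivity analysis leaves the number of imputations open at 5 to 20 with no seed, so near p = 0.05 its p-value moves with choices that the plan has not fixed

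*SAP*

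**What the plan says.** The primary analysis (SAP 3.14) is a mixed model for repeated measures in the ITT population, and SAP 3.14.2 confirms that "though no imputations will be used in the primary analysis". That section then plans two sensitivity analyses. One refits the model with data up to Week 24 only and involves no imputation. The other is the subject here: "Missing data points will be imputed using a multiple imputation method". On the number of imputations the text reads "This method will generate m completed data sets", with m given as 5 to 20, and the supplied sections give no rule for choosing within that range, no seed and no imputation model.

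The analysis is conditional. It runs "when > 5% of data points in each group have missing information", which the same sentence glosses as "<57 patients per group have information".

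Two other places bear on how the result will be read. SAP 3.1.1 sets the general convention: "Two-tailed tests will be performed for all analyses that use statistical testing with a significance level of" 0.05, with p-values shown to four decimals. SAP 3.2 tests everything beyond the primary analysis at a nominal 5% and ties study success to the primary analysis alone. Protocol 12.4.1 describes the check differently: "missing data points will be imputed using appropriate interpolation methods". The move to multiple imputation is not among the changes from protocol listed in SAP section 5.

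**The concern.** A pooled multiple-imputation estimate carries random error from the finite number of imputed data sets. With m between 5 and 20, that error is large enough to move a p-value in its second decimal when it lies near 0.05. Two analysts who follow the SAP exactly, one with m=5 and one with m=20, or both with the same m and different seeds, can obtain p-values on either side of 0.05 from the same data. This noise says nothing about the missing data, which is what the analysis is meant to probe. It matters most when the primary result is borderline, which is when a reader looks hardest at a sensitivity analysis.

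**Working it through.** **Inputs from the documents.** m = 5 to 20 (SAP 3.14.2). Two-sided alpha 0.05 (SAP 3.1.1). Difference 4, SD 8, 60 completers per group, at least 136 randomized 1:1, so 68 per arm (SAP 2.6).

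**Assumption.** The documents give no FMI. The main figure uses 0.08, which suits roughly 8-14% missing at Week 24 with between-visit correlations of 0.4-0.6. Higher values are shown alongside.

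**Step 1: the plan's own figure.** The count in the trigger is 0.95 × 60 = 57, so it is based on the 60 planned completers. The analysis is in the ITT cohort, with 68 per arm:
- Percentage form: 5% of 68 is 3.4, so it is met at 4 or more missing (64 or fewer observed).
- Count form: fewer than 57 observed means 12 or more missing, and 12/68 = 17.6%.
- At 60 observed per arm, 8/68 = 11.8% are missing. The percentage form fires and the count form does not.

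**Step 2: seed noise by formula.** The pooled z statistic varies between seeds with SD of about sqrt(FMI/m). For a true p of 0.05, z = 1.96, and the 95% seed range is 1.96 ± 1.96 × sqrt(FMI/m). At FMI 0.08:

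| m | SD of z | z range | p range |
|---|---|---|---|
| 5 | sqrt(0.016) = 0.126 | 1.71-2.21 | 0.027-0.087 |
| 20 | sqrt(0.004) = 0.063 | 1.84-2.08 | 0.037-0.066 |
| 200 | sqrt(0.0004) = 0.020 | 1.92-2.00 | 0.046-0.055 |

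Within the permitted range, m=5 is sqrt(20/5) = 2 times as noisy as m=20. At FMI 0.176 the p ranges are 0.020-0.111 (m=5), 0.032-0.076 (m=20) and 0.044-0.057 (m=200).

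The treatment estimate itself moves little. Its standard error is 8 × sqrt(2/68) = 1.37 points, so at FMI 0.08 the seed SD is 1.37 × 0.126 = 0.17 points at m=5 and 1.37 × 0.063 = 0.09 at m=20.

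**Step 3: simulation.** Settings: 68 per arm, SD 8, five visits, monotone dropout, regression imputation by arm, Rubin's rules with small-sample degrees of freedom, four data sets per setting and 1,500 re-draws per data set. The data sets were chosen so that the many-imputation p was 0.035-0.048. In each cell the first figure is for visit correlation 0.3 and the second for 0.6.

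| Missing | m | 95% seed range of p | Seeds with p > 0.05 |
|---|---|---|---|
| 12% | 5 | 0.019-0.097; 0.022-0.080 | 37%; 32% |
| 12% | 20 | 0.028-0.062; 0.031-0.057 | 20%; 16% |
| 12% | 100 | 0.034-0.049; 0.036-0.048 | 7%; 5% |
| 18% | 5 | 0.014-0.120; 0.019-0.096 | 40%; 39% |
| 18% | 20 | 0.024-0.067; 0.028-0.062 | 23%; 22% |
| 18% | 100 | 0.032-0.050; 0.035-0.049 | 7%; 7% |

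The 18% rows are close to where the count form of the trigger would first allow the analysis to run.

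**Step 4: how often it would matter.** Steps 2 and 3 look only at results already near 0.05. Across all trials under the planned effect, z is about normal with SD 1 and mean 4/(8 × sqrt(2/n)), which is 2.74 at n=60 and 2.92 at n=68. Given z, a seed is significant with probability q = Φ((z − 1.96)/sqrt(FMI/m)), and two seeds disagree with probability 2q(1 − q). Averaged over z at FMI 0.08, disagreement is 3.6-4.2% at m=5 and 1.8-2.1% at m=20. At FMI 0.23 it is at most 7.1% and 3.6%. With no true effect and FMI 0.08 it is 1.7% and 0.8%.

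Away from 0.05 the reading does not change: at FMI 0.08 and m=5, a true p of 0.01 ranges 0.005-0.020 and a true p of 0.20 ranges 0.126-0.301.

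**The case against.** The strongest reply is that nothing formal depends on this analysis. Success rests on the ITT mixed model, and no sentence requires the imputation run to reach p < 0.05. The SAP also plans other supporting analyses without imputation: the Week-24-only refit, a refit with Trikafta and pandemic covariates, and analyses in the per-protocol and two exacerbation populations. This stands, and it limits the point to a small one. A reader might infer that the trial's verdict could turn on a random seed; SAP 3.2 and 3.14 rule that out.

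A reader might also infer that the sponsor means to pick m after seeing results. The open range permits this but does not show any such intention. The mock tables in SAP section 7 are not in the supplied text, and their footnotes might fix m.

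Nor do the documents say that 16 of 136 patients will be missing. SAP 2.6 does not expect dropout above 10%, 120 completers is a minimum, 136 reflects rounding up to a multiple of 8, and Protocol section 12 asks that patients who stop treatment still be followed. Sixteen is a ceiling. If the count form of the trigger governs, the analysis would not run at all at 60 completers per group.

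Finally, a larger m does not remove the noise. At m=200 and FMI 0.08, a true p of 0.049 still exceeds 0.05 in about a third of seeds. The fixed seed is what makes the result reproducible; the larger m makes it depend less on that seed.

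**Conclusion.** The point holds as a minor one. Given that the analysis runs and its p-value is near 0.05, the reported p-value depends noticeably on m and the seed, and neither is fixed in the supplied text. The exact ranges rest on the assumed FMI, but the conclusion holds throughout the range examined (10-25% missing, visit correlation 0.3-0.6, FMI 0.06-0.23). There, among data sets with a many-imputation p of 0.035-0.048, 28-48% of seeds gave p > 0.05 at m=5 and 11-34% at m=20. The disagreement between the two trigger forms is a definite inconsistency in the same paragraph and needs no assumption beyond 68 per arm.

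**What to change.** In SAP 3.14.2, replace the range with one fixed larger value, for example m=100 or m=200, and write the seed into the SAP before unblinding. Report the Monte Carlo error of the pooled estimate beside the result. In the same edit, state one trigger, as either a percentage or a count, and base it on the number randomized per arm. Add the change from the protocol's interpolation wording to SAP section 5. Fixing m does not supply the imputation model, which should be stated too.

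The cost is a few lines of SAP text and a short extra run time for about 136 patients. No patients, visits or data are needed.

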3.15 Analysis of the Secondary Endpoints

For all secondary efficacy endpoints, all the analysis will be based on data obtained at Week 24 or cumulated up to Week 24

Pre-defined Clinical Parameters:

- Count data variables: the number of antibiotic treatments, the number of days of antibiotic treatment (other than chronic inhaled antibiotics already started prior to trial or oral chronic azithromycin, in summary, any antibiotic change required to address worsening of CF symptoms) and the number of PEx and protocol-defined PEx will be tabulated by treatment group and compared using an appropriate count data model, e.g., Mixed ANOVA model (if assumptions of normality and homogeneity of variance appear acceptable), Poisson regression, negative binomial regression, zero-inflated regression, etc., depending on their distribution. The analysis of the number of protocol-defined PEx will also consider the type of antibiotic

prescribed (I.V. vs. oral) and the time spent on study as well as other covariates described below for the time to event data.

- Time to event data variables: the time to first antibiotic use, the time to first PEx and protocol-defined PEx, the time interval between IV antibiotic-treated PEx episodes will be tabulated by treatment group and compared using a Cox proportional hazards model. The model will include treatment group as main effect with covariates for FEV₁ percent predicted category (<70% versus ≥70% predicted), PEx number category in prior year (≤3 versus > 3 PEx episodes), and co-administration or not of Kalydeco® (ivacaftor), Orkambi® (ivacaftor/lumacaftor), Symdeko® (ivacaftor/tezacaftor) or another commercially available CFTR modulator product (all as per entry stratification). A patient without exacerbation before withdrawal or completion of the study is considered censored at the time of withdrawal or completion of the study. If the proportional hazards assumption is violated, a stratified analysis will be conducted using stratified Cox regression. Additionally, Kaplan-Meier methods will be used to produce graphical presentations of the survival (exacerbation-free survival) by treatment group and to estimate cumulative exacerbation-free survival rates by treatment group.
- Relative change (in %) in FEV₁ percent predicted from Baseline to Week 24: analysis of this variable will be similar to that of the primary analysis of the primary efficacy endpoint, i.e. repeated measures mixed model.
- Body weight and BMI changes from Baseline/Screening will be summarized using descriptive statistics by treatment group and compared between treatments using a linear mixed model similar to what is described under [Section 3.14](#), with the addition of the baseline parameter (Weight or BMI at baseline) as covariate in the model.

Quality of Life Endpoints:

- Quality-of-life data will be derived from the questionnaires according to the corresponding scoring manuals and will be summarized by treatment group. Patients' health state will be derived from the CFQ-R questionnaire, including the extracted CFQ-R respiratory domain, a separate endpoint. Additional exploratory health condition will be evaluated by the Matouk Disease Score. Data will be summarized by treatment group using descriptive statistics.

Analysis of the absolute change from baseline for the CFQ-R (overall and respiratory domain) as well as the Matouk Disease Score will be performed similarly to that of the primary efficacy endpoint with the addition of the CFQ-R score at baseline as a covariate for the analysis of the CFQ-R variables.

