12.4.2 Analysis of Secondary Efficacy Endpoints

For all secondary efficacy endpoints, the primary analysis will be based on data obtained at Week 24 or cumulated up to Week 24.

Pre-defined Clinical Parameters:

- Count data variables: The time to first antibiotic use, the number of antibiotic treatments, the number of days of antibiotic treatment (other than chronic inhaled antibiotics already started prior to trial or oral chronic azithromycin) and the number of protocol-defined PEx will be tabulated by treatment and compared using Count regression will be used for the group comparison of the number of antibiotic treatments and the number of days of antibiotic treatment. The number of protocol-defined PEx will take

into account in the model of the time spent on study and considering the same covariates as those described below for the time to event data.

- Time to event data variables: The time to first protocol-defined PEx, the time interval between IV antibiotic-treated PEx episodes will be tabulated by treatment and compared using a Cox proportional hazards regression analysis. The model will include treatment as main effect with covariates for age category at baseline, FEV₁ % predicted category (as per entry stratification), PEx number category in prior year (as per entry stratification). A patient without exacerbation before withdrawal or completion of the study is considered censored at the time of withdrawal or completion of the study. If the proportional hazards assumption is violated, a stratified analysis will be conducted using stratified Cox regression. Additionally, Kaplan-Meier methods will be used to produce graphical presentations of the survival (exacerbation-free survival) by treatment and to estimate cumulative survival rates by treatment.
- Relative change (in %) in FEV₁ % predicted from baseline to Week 24: Analysis of this variable will be similar to that of the primary analysis of the primary efficacy endpoint
- Body weight and BMI changes from baseline/screening will be summarized using descriptive statistics by treatment and compared between treatments using a linear mixed-effects model with treatment as fixed effect; visit and treatment-by-visit interaction as random effects; and adjustment for FEV₁ % predicted category (as per entry stratification), PEx number category in prior year (as per entry stratification) and weight or BMI at baseline as covariates.

Pharmacodynamic Endpoints:

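### Time on study is specified for only one of the four count endpoints, leaving the antibiotic counts open to bias if withdrawal differs between arms

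*SAP*

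**What the plan says.** SAP 3.15 bases the secondary analyses on results that are "based on data obtained at Week 24 or cumulated up to Week 24". Its count-data paragraph names four variables: antibiotic treatments, antibiotic days, PEx and protocol-defined PEx. They are to be "compared using an appropriate count data model, e.g., Mixed ANOVA model (if assumptions of normality and homogeneity of variance appear acceptable". The other models offered as examples are Poisson, negative binomial and zero-inflated regression, and the choice depends on the observed distribution.

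The next sentence narrows to one endpoint: "The analysis of the number of protocol-defined PEx will also consider the type of antibiotic". The two antibiotic types it distinguishes are IV and oral. For that same endpoint, and no other, it then adds "the time spent on study as well as other covariates described below for the time to event data". Those other covariates are the three stratification factors listed for the Cox models.

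Protocol 12.4.2 is similar. It says that "Count regression will be used for the group comparison of the number of antibiotic treatments and the number of days of antibiotic treatment", with no exposure term. For protocol-defined PEx alone it takes "into account in the model of the time spent on study". Overall PEx is not a protocol count endpoint; the SAP added it (SAP section 5). Neither document defines a rate, an offset or an exposure adjustment for the antibiotic counts.

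**The concern.** A cumulative count depends on how long the patient was observed. Someone who leaves at Week 6 with no antibiotic course is scored like someone who completed 24 weeks with none. The authors evidently saw this for protocol-defined PEx but did not carry it to the other counts, and one listed model, ANOVA on the count, has no exposure offset.

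The plan allows follow-up to vary:

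- The ITT set keeps randomised patients with completed baseline evaluations whether or not they were treated (SAP 3.3).
- Patients who withdraw after Baseline are not replaced (SAP 2.7.3).
- Some drug-related serious events lead to withdrawal from the study (Protocol 8.3).
- A patient who stops treatment for toxicity may attend only one further visit, four weeks after the last dose (Protocol 8.4).

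At stake is the reading of the antibiotic-use endpoints. If one arm loses more follow-up, its lower count could be read as a treatment effect.

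**Working it through.** **1. The plan's own withdrawal figure.** SAP 2.6 gives 60 completers per group (120 in total) and dropout of at most 10%. 120 / (1 − 0.10) = 133.3, rounded up to 134. The next multiple of 8 is 136, or 68 per arm. The figure reproduces. It is an overall allowance and is not split by arm. No power is stated for any count endpoint.

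**2. Expected ratio with no exposure term.** Let w be the share of an arm that withdraws and t the mean fraction of the 24 weeks those patients complete. Mean exposure is E = 1 − w(1 − t). With equal true event rates, the expected ratio of mean counts is E(first arm) / E(second arm). The values of w and t are assumptions. All rows average 10% or less overall.

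| Withdrawal, first vs second arm | Exit at 12 weeks (t = 0.5) | 6 weeks (t = 0.25) | 3 weeks (t = 0.125) |
|---|---|---|---|
| 10% vs 10% | 1.00 | 1.00 | 1.00 |
| 10% vs 0% | 0.95 | 0.925 | 0.91 |
| 15% vs 5% | 0.95 | 0.92 | 0.91 |
| 20% vs 0% | 0.90 | 0.85 | 0.825 |

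For 15% vs 5% at mid-study: (1 − 0.15 × 0.5) / (1 − 0.05 × 0.5) = 0.925 / 0.975 = 0.949. With the arms exchanged it is 0.975 / 0.925 = 1.054, so the bias follows the arm with less follow-up and not a particular treatment.

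**3. Size against sampling error.** For an over-dispersed count with mean m per patient and dispersion k, the standard error of the log ratio is √[2(1/m + k)/68]. The only rate anchor in the documents (Protocol section 6) is a chance of about 30% of an IV-treated PEx in 24 weeks for patients with such an event in the prior year: m = −ln(0.70) ≈ 0.36. Dispersion k = 0.5 and a second rate, m = 1.0, are assumed.

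- m = 0.36: √[2(2.78 + 0.5)/68] = 0.31.
- m = 1.0: √[2(1 + 0.5)/68] = 0.21.
- Bias at 15% vs 5%: ln(0.949) ≈ −0.052, which is 0.17 and 0.25 standard errors respectively.

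**4. Simulation with no true effect.** 68 per arm, gamma-Poisson counts with k = 0.5, near-uniform withdrawal times, 4,000 runs, log rate ratio with a robust standard error. The table shows how often the arm with more withdrawal is declared better (nominal 2.5%), at assumed rates of 0.36, 1.0 and 1.5 events per 24 weeks.

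| Withdrawal | No exposure term | Log-time offset |
|---|---|---|
| 10% vs 10% | 2.1%, 2.5%, 3.0% | 2.0%, 2.5%, 2.9% |
| 15% vs 5% | 3.9%, 5.2%, 4.9% | 2.5%, 3.0%, 2.4% |
| 20% vs 0% | 5.4%, 7.1%, 7.5% | 2.7%, 2.4%, 2.2% |

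Without the exposure term, the mean estimated ratio is 0.94 to 0.95 at 15% vs 5% and 0.90 at 20% vs 0%. With the offset it is 0.99 to 1.01 throughout. The simulation describes event counts. It does not describe antibiotic days, which arrive in clumps.

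**The case against.** A reader might infer that three endpoints will be compared as raw counts and that early withdrawal will therefore look like benefit from LAU-7b. The documents do not support that reading, for three reasons.

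- **Silence is not a decision.** A Poisson or negative binomial model chosen as appropriate could carry an offset. The ANOVA route is conditional on normality and equal variance, which sparse counts seldom meet.
- **Overall PEx is ambiguous.** The sentence that brings in time on study also brings in IV versus oral antibiotic. Protocol-defined PEx requires parenteral treatment (Protocol 9.3.1; SAP 3.3), so an oral category makes sense only for overall PEx. The sentence may have been meant for both.
- **The direction is not fixed.** Between-arm bias needs unequal withdrawal and can favour either arm.

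There are also mitigations. Patients who stop treatment should still be followed at scheduled visits, or for at least a month (Protocol section 12). The Cox analyses state censoring at withdrawal for patients without exacerbation. The per-protocol set needs at least five cycles, so follow-up there is closer to equal, though at the price of selection. The secondary endpoints are tested at nominal 5% for signal detection (SAP 3.2).

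These arguments limit the size of the problem. They do not remove the gap for antibiotic treatments and antibiotic days, where neither document states an adjustment. The Cox models cover first events and say nothing about total courses or days. The IV-versus-oral puzzle is itself a reason to rewrite the sentence.

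**Conclusion.** The point holds as an incomplete and selective specification. Exposure adjustment and covariates are stated for protocol-defined PEx only. They are absent for antibiotic treatments and antibiotic days and unclear for overall PEx, and a model with no exposure offset is permitted. If the text is followed literally and withdrawal differs by arm, the comparison is biased towards the arm with less follow-up.

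The size is modest. It is about 5% on the ratio at an assumed 15% versus 5% with mid-study exits, or roughly a quarter of a standard error or less under the assumed rates and dispersion. Withdrawal by arm, its timing, the dispersion and the higher event rates are all assumptions. Confidence is high on the textual gap and much lower on whether any bias would arise.

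An offset also assumes that leaving is unrelated to a patient's event risk. It would not remove bias from patients who leave because they are exacerbating.

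**What to change.** In SAP 3.15, give all four counts the same structure: a log-link count model with treatment, the three stratification factors and an offset of log(days on study, truncated at Week 24), so that the denominator matches the counting window. Count the first day inclusively, so that the offset is defined for a patient who leaves on Day 1.

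- Antibiotic treatments, overall PEx and protocol-defined PEx: negative binomial regression.
- Antibiotic days: a pre-specified over-dispersed or zero-inflated model with the same offset. Negative binomial is not clearly right here, because Protocol 9.3.3 sets PEx antibiotic courses at seven days or more, which gives many zeros and clumps of days.
- Delete the ANOVA option.
- State which PEx count the IV-versus-oral term belongs to.
- Report events, and antibiotic days, per patient-time by arm alongside the model estimates.

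The cost is SAP wording and matching table shells. The dates needed are already collected.
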